### **7.8.3 Vital signs**

The analyses of vital signs (blood pressure and pulse rate) will be descriptive in nature. Descriptive statistics of vital signs over time and for the difference from baseline (see [Section 6.7](#)) will be provided.

Unscheduled measurements of vital signs will be assigned to planned time points in the same way as described above for laboratory data. However, for vital signs, descriptive statistics will be calculated by planned time point based on the last value of the subject at that planned time point (or assigned to that planned time point). If the time of measurement is missing for a scheduled post-baseline measurement, the scheduled measurement will be used in calculation of descriptive statistics (as time difference between scheduled and unscheduled cannot be assessed).

If the time of measurement is missing for an unscheduled measurement, this measurement will be listed but will be ignored for the calculation of descriptive statistics.

Clinically relevant findings in vital signs data will be reported as baseline conditions (prior to first administration of study treatment) or as AEs (after first administration of study treatment) if judged clinically relevant by the investigator, and will be analyzed as such.

### **7.8.4 ECG**

Abnormal findings in ECG will be reported as baseline conditions (at screening) or as AEs (during the trial) if judged clinically relevant by the investigator, and will be analyzed as such. No separate listing or analysis of ECG data will be prepared.

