	2		24:00	09:00	Breakfast (voluntary) ³ , discharge from trial site	B	x				x
	3		47:00	08:00	Ambulatory visit		x				x
	4		71:00	08:00	Ambulatory visit		x				x
	6		119:00	08:00	Ambulatory visit		x				x
	8		167:00	08:00	Ambulatory visit		x				x
	10		215:00	08:00	Ambulatory visit	C	x				x

- Subject must be informed and written informed consent obtained prior to starting any screening procedures. Screening procedures include physical examination, check of vital signs, ECG, safety laboratory (including drug screening), demographics (including determination of body height and weight, smoking status and alcohol history), relevant medical history, concomitant therapy and review of inclusion/exclusion criteria. Pharmacogenetic samples will be collected if needed.
- The time is approximate; the procedure is to be performed and completed within the 3 h prior to BI 425809 drug administration.
- If several actions are indicated at the same time, the intake of meals will be the last action.
- See [Flow Chart \(cont.\)](#) on next page
- AEs and concomitant therapies will be recorded throughout the trial, but will be specifically asked for at the times indicated in the [Flow Chart](#) above.
- Only applicable for Flow Chart for Treatment T
- Only applicable for Flow Chart for Treatment T
- Letters A, B, C and D (in Flow Chart below) define different sets of safety laboratory examinations (for details refer to Section [5.2.3](#)).
- Including urine drug screening and alcohol breath test

FLOW CHART (cont.)

[figure not shown]
Period	Visit	Day	Planned time (relative to BI 425809 administration) [h:min]	Approximate clock time of actual day [h:min]	Event and comment	Safety laboratory ⁸	PK plasma (BI 425809)	PK plasma (fluconazole)	12-lead ECG	Vital signs (BP, PR)	Questioning for AEs and concomitant therapy ⁵
Treatment T (Fluconazole multiple dose + BI 425809 single dose)	3	-4	-97:00	08:00	Fluconazole administration				x		x
		-3	-73:00	08:00	Fluconazole administration						x
		-2	-49:00	08:00	Fluconazole administration						x
		-1	-25:00	08:00	Fluconazole administration	C					x
		1	-2:00	07:00	Admission to trial site	B ^{2,9}	x ²		x ²	x ²	x ²
			-1:00	08:00	Fluconazole administration			x ⁷			
			0:00	09:00	Administration of BI 425809						
			0:30	09:30			x				
			1:00	10:00			x				
			1:30	10:30			x				
			2:00	11:00	240 mL fluid intake		x				
			3:00	12:00			x			x	
			4:00	13:00	240 mL fluid intake, Lunch ³		x				x
			5:00	14:00			x				
			6:00	15:00			x				

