QTcF increased during fluconazole by 11.4 ± 6.0 ms (range 5-23 ms, $P < 0.01$). QTcF or relative change in QTcF did not correlate with fluconazole concentration. However, in the present trial ECGs were done primarily for safety reasons and not to evaluate effects on QTc. Thus, the authors obtained only single ECG recordings, the screening ECG could be obtained later in the day, and participants were not required to be fasting at screening and on the fifth day of fluconazole. Thus, also circadian variability or food effects may have influenced QTc.

Clinical safety in patients:

According to the German “Fachinformation”, the most frequently ($\geq 1/100$ to $< 1/10$) reported adverse reactions are headache, abdominal pain, diarrhoea, nausea, vomiting, alanine aminotransferase increased, aspartate aminotransferase increased, blood alkaline phosphatase increased and rash (see also Section [1.4.3.2](#)).

Fluconazole (Diflucan[®]) has been associated with rare cases of serious hepatic toxicity including fatalities, primarily in patients with serious underlying medical conditions. In cases of fluconazole associated hepatotoxicity, no obvious relationship to total daily dose, duration of therapy, sex or age of patient has been observed. Fluconazole hepatotoxicity has usually been reversible on discontinuation of therapy.

Fluconazole causes QT prolongation via the inhibition of Rectifier Potassium Channel current (I_{Kr}). During post-marketing surveillance, there have been very rare cases of QT prolongation and torsades de pointes in patients taking Diflucan. These reports included seriously ill patients with multiple confounding risk factors, such as structural heart disease, electrolyte abnormalities and concomitant treatment that may have been contributory.

Fluconazole 200 mg to 400 mg daily has no clinically significant effect on endogenous steroid levels or on ACTH stimulated response in healthy male volunteers.

For a detailed description of the fluconazole profile, please refer to the German ‘Fachinformation’ [[R21-2282](#)].

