1.4.3.2 Risks related to the administration of fluconazole

Fluconazole (Diflucan[®]) is a market-approved drug. The dose used in this trial (400 mg qd for 13 days) is within the therapeutic range used for patients to treat fungal infections [[R21-2282](#)].

Based on the German ‘Fachinformation’ for Diflucan[®], the following adverse reactions have been observed and reported during treatment with Diflucan with the following frequencies: Very common ($\geq 1/10$); common ($\geq 1/100$ to $< 1/10$); uncommon ($\geq 1/1,000$ to $< 1/100$); rare ($\geq 1/10,000$ to $< 1/1,000$); very rare ($< 1/10,000$), not known (cannot be estimated from the available data).

- Common: Headache, abdominal pain, vomiting, diarrhea, nausea, alanine aminotransferase increased, aspartate aminotransferase increased, blood alkaline phosphatase increased, rash
- Uncommon: Anaemia, decreased appetite, somnolence, insomnia, seizures, paraesthesia, dizziness, taste perversion, vertigo, constipation, dyspepsia, flatulence, dry mouth, cholestasis, jaundice, bilirubin increased, drug eruption, urticarial, pruritus, increased sweating, myalgia, fatigue, malaise, asthenia, fever
- Rare: Agranulocytosis, leukopenia, thrombocytopenia, neutropenia, anaphylaxis, hypercholesterolaemia, hypertriglyceridaemia, hypokalemia, tremor, torsade de pointes, QT prolongation, hepatic failure, hepatocellular necrosis, hepatitis, hepatocellular damage, toxic epidermal necrolysis, Stevens-Johnson syndrome, acute generalized exanthematous-pustulosis, dermatitis exfoliative, angioedema, face oedema, alopecia
- Not known: Drug reaction with eosinophilia and systemic symptoms (DRESS)

Risk mitigation hepatic injury:

- During fluconazole dosing phase laboratory liver parameters will be regularly assessed
- Only subjects with liver parameters AST, ALT and GGT within normal range will be allowed to participate in the trial (see Section [3.3.3](#))
- In case of relevant increase in liver enzymes or hepatic injury (DILI), subjects will discontinue trial treatment (see Section [3.3.4.1](#))

Risk mitigation QT prolongation:

- Subjects with baseline disease (such as pro-arrhythmic conditions) will be excluded from the trial
- No concomitant therapy prolonging the QT interval will be allowed
- During fluconazole dosing phase ECG will be assessed regularly for potential QT prolongation
- Laboratory tests (including determination of potassium levels) will be performed

Risk mitigation dermatological reaction:

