5.2.4 Electrocardiogram

Twelve-lead ECGs (I, II, III, aVR, aVL, aVF, V1 - V6) will be recorded using a computerised electrocardiograph ([REDACTED]) at the times provided in the [Flow Chart](#).

To achieve a stable heart rate at rest and to assure high quality recordings, the site personnel will be instructed to assure a relaxed and quiet environment, so that all subjects are at complete rest.

All ECGs will be recorded for a 10 sec duration after subjects have rested for at least 5 min in a supine position. ECG assessment will always precede all other study procedures scheduled for the same time to avoid compromising ECG quality.

All ECGs will be stored electronically on the Muse CV Cardiology System ([REDACTED]) ([REDACTED]). Electrode placement will be performed according to the

method of Wilson, Goldberger and Einthoven modified by Mason and Likar (hips and shoulders instead of ankles and wrists).

All locally printed ECGs will be evaluated by the investigator or a designee. Abnormal findings will be reported as AEs (during the trial) or baseline conditions (at screening) if assessed to be clinically relevant by the investigator. Any ECG abnormalities will be carefully monitored and, if necessary, the subject will be removed from the trial and will receive the appropriate medical treatment.

ECGs may be repeated for quality reasons (for instance, due to alternating current artefacts, muscle movements, or electrode dislocation) and the repeated ECG will be used for analysis. Additional (unscheduled) ECGs may be collected by the investigator for safety reasons.

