Previous and concomitant therapies will be presented per treatment group without consideration of time intervals and treatment periods.

Laboratory data will be compared to their reference ranges. Values outside the reference range as well as values defined as possibly clinically significant will be highlighted in the listings. Additionally, differences from baseline will be evaluated.

Vital signs or other safety-relevant data will be assessed with regard to possible on-treatment changes from baseline.

Relevant ECG findings will be reported as AEs.

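### ECG values are neither listed nor summarised, so a QTc shift on fluconazole reaches the report only as an investigator-judged adverse event; the documents' general safety statements imply more

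*SAP*

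**What the plan says.** SAP 7.8.4 gives the only route by which an ECG result is reported: "Abnormal findings in ECG will be reported as baseline conditions (at screening) or as AEs (during the trial) if judged clinically relevant by the investigator". It then adds: "No separate listing or analysis of ECG data will be prepared". Protocol 7.3.4 has the same rule in short form: "Relevant ECG findings will be reported as AEs".

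On the risk, Protocol 1.2.2 is direct: "Fluconazole causes QT prolongation via the inhibition of Rectifier Potassium Channel current". It also reports from a cited healthy-volunteer study that "QTcF increased during fluconazole by 11.4" ± 6.0 ms, with a range of 5 to 23 ms. Protocol 1.4.3.2 gives the mitigation: "During fluconazole dosing phase ECG will be assessed regularly for potential QT prolongation".

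The Flow Chart schedules seven ECGs per subject: at screening, before BI 425809 in period 1, on Day -4 of period 2, before dosing on Day 1 of period 2, at 24 h, at 167 h (Day 8) and at the end of the trial. Laboratory data and vital signs, by contrast, receive descriptive statistics over time and for change from baseline (SAP 7.8.2 and 7.8.3).

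**The concern.** The ECG is the measurement tied to a risk that the protocol names and quantifies, yet it is the only scheduled numerical safety measurement with no planned summary. The adverse-event route depends on judging one subject's tracing at a time. It suits a marked individual abnormality and is insensitive to a moderate shift shared by most subjects. The visible text sets no numerical on-treatment QTc threshold for an adverse event. The only figure is the 450 ms entry limit in exclusion criterion 20.

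If the cited effect recurs, the report could show no ECG-related adverse events and give the reader no values to check. The recordings will exist in electronic form (Protocol 5.2.4).

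**Working it through.** The plan has no figure of its own to reproduce here. The check compares the texts, reads the ECG column of the Flow Chart, and adds one illustrative calculation.

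**1. Texts side by side**

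| Place | What it implies for ECG |
|---|---|
| SAP 7.8.4 | No listing, no analysis; adverse events only |
| Protocol 7.3.4, ECG sentence | Adverse events only |
| Protocol 7.1 with 2.2.2.3 | Descriptive statistics for the listed safety parameters, which include the 12-lead ECG |
| Protocol 7.3.4, treatment assignment | ECG measurements are allocated to treatments alongside vital signs and laboratory values |
| Protocol 7.3.4, vital signs sentence | Other safety-relevant data are also examined for on-treatment change from baseline |
| SAP 7, opening | Every subject's individual values are listed |

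Protocol 7.1 cites section 2.2.2.2, while the visible safety list is 2.2.2.3. I take this as a cross-reference slip. The first two rows conflict with the other four.

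**2. Could the cited shift escape notice?** A subject with a QTc below 450 − 11.4 = 438.6 ms before fluconazole stays under 450 ms after the mean cited rise. With the largest cited rise the figure is 450 − 23 = 427 ms. The 450 ms value is used only as a reference point, because it is an entry criterion and not an on-treatment rule.

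**3. Which ECG is a usable baseline?** Protocol 5.2.4 says that "ECG assessment will always precede all other study procedures scheduled for the same time to avoid compromising ECG quality", so the Day -4 recording comes before the first fluconazole dose. At the minimum wash-out it falls 16 × 24 − 97 = 287 h after the first BI 425809 dose. That is 287/44 = 6.5 half-lives, so about 0.5^6.5 ≈ 1% remains. SAP 6.7 takes the last value before BI 425809 as baseline. In period 2 that is the Day 1 pre-dose ECG, after four days of fluconazole, and it would hide most of the effect.

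**4. What differs between the period 2 recordings?**

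| Time point | Clock time | Fluconazole doses so far | Time since last dose | Fasting required |
|---|---|---|---|---|
| Day -4 | 08:00 | 0 | – | no |
| Day 1 pre-dose | 07:00 | 4 | about 23 h | yes |
| 24 h | 09:00 | 6 | 1 h | yes |
| 167 h | 08:00 | 11 | 24 h | no |

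Protocol 1.2.2 puts the fluconazole peak at 0.5 to 1.5 h. Day 1 pre-dose is therefore at trough and 24 h is near peak. Treatment R has no ECG after BI 425809.

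**5. Illustrative precision.** The inputs are n = 15 (Protocol 7.7) and 6.0 ms read as a standard deviation. That reading fits the cited range. Taking the 12 subjects of the study described just before the figure, a range of 18 ms allows a standard deviation of at most 9 × √(12/11) = 9.4 ms. If 6.0 were a standard error, the standard deviation would be 6 × √12 = 20.8 ms, which is impossible.

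The half-width is t(0.95, n−1) × SD/√n:
- n = 15, SD 6.0: 1.761 × 6.0/3.873 = 2.73 ms (90% CI); the 95% CI gives 3.32 ms.
- n = 12, SD 6.0: 3.11 ms (90% CI).
- n = 15, SD doubled to 12.0: 2 × 2.73 = 5.46 ms (90% CI).

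**The case against.** The strongest reply is that the SAP follows the protocol. Protocol 7.3.4 has a sentence specific to ECG, a specific rule normally overrides a general one, and SAP section 4 declares accordance with the protocol. This stands in part. A reader might infer that the SAP dropped an ECG analysis that the protocol had planned, but the documents do not support that. The conflict begins inside the protocol, and the SAP repeats it and adds its own in section 7.

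Second, the trial is a pharmacokinetic study, the fluconazole effect is already known, and ECGs are there for safety. Protocol 5.2.4 has each printed ECG evaluated by the investigator, with abnormalities followed up. This stands. The commitment in Protocol 1.4.3.2 concerns monitoring, and it is met. It would be wrong to say that QT is unmonitored or that the recordings go unused.

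Third, a reader might infer that the schedule separates the two drugs, with Day -4 to Day 1 showing fluconazole and Day 1 to Day 2 showing BI 425809. The documents do not support the second contrast. It runs from fluconazole trough to near its peak with two further doses in between, and no post-dose ECG on BI 425809 alone exists for comparison.

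Fourth, the 11.4 ms figure comes with warnings in Protocol 1.2.2: single recordings, made for safety, open to circadian and food effects. The preceding study description also involves ciclosporin, rivaroxaban and a fluconazole loading dose. This stands, and similar limits apply here. It rules out reading a narrow interval as proof of a drug effect. It does not justify withholding the values.

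**Conclusion.** The point holds as a reporting gap that is modest in size and cheap to close. Both documents carry an adverse-event-only rule for ECG that does not fit their general statements on safety analysis and listings, or the prominence that the protocol gives to QT prolongation. A mean rise of about 11 ms could recur and be absent from the report.

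The conclusion rests on reading the ECG-specific sentences as governing, on taking the section cited in Protocol 7.1 to mean the safety list in 2.2.2.3, and on there being no on-treatment QTc threshold in the redacted text. The 2.7 ms half-width is an illustration that depends on a borrowed standard deviation. It measures sampling error only, not differences in fasting state, clock time or time since the last fluconazole dose. Changes at 24 h and 167 h would reflect both drugs together.

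**What to change.** Replace the last sentence of SAP 7.8.4 with:

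- One listing of heart rate and QTcF by subject and time point.
- One descriptive table of QTcF and its change from the Day -4 ECG, at period 2 Day 1 pre-dose, 24 h and 167 h. Add counts in pre-stated categories, for example above 450, 480 and 500 ms, and rises above 30 and 60 ms. These are suggestions; apart from the 450 ms entry limit, the documents define none.
- A statement that Day -4 is the ECG baseline, as an exception to SAP 6.7.
- The correction method. The protocol's abbreviation list allows Fridericia or Bazett, and 5.2.4 names neither. Fridericia matches the cited figure.
- A rule for unscheduled ECGs. Protocol 5.2.4 already says that a recording repeated for quality reasons replaces the first.
- A footnote that the output is descriptive, from single ECGs whose fasting state and time since the last fluconazole dose differ, and that it does not isolate BI 425809. Include no Day 1 to Day 2 contrast.

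Record the addition in SAP section 4, since it goes beyond the ECG sentence in Protocol 7.3.4, and reconcile it with the listing rule in SAP 7. No trial procedure changes. The cost is a transfer of stored ECG intervals, one listing and one table. The downside is that single recordings are noisy, so small shifts should not be interpreted.

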## **7.8.5 Others**

### **7.8.5.1 Physical examination**

Physical examination findings will be reported as relevant medical history/baseline condition (if a condition already exists before first administration of study treatment) or as AE (if condition emerges after first administration of study treatment) and will be summarized as such. No separate listing or analysis of physical examination findings will be prepared.

### **7.8.5.2 Body weight**

Body weight will only be measured at screening and therefore will only be listed.

[figure not shown]
## **8. TIMEPOINT OF RELEASE OF TREATMENT INFORMATION**

The treatment information will be loaded into the trial database at trial initiation.

## 11. HISTORY TABLE

Table 11: 1 History table

Version	Date (DD-MMM-YY)	Author	Sections changed	Brief description of change
Final	10-FEB-2022		None	This is the final TSAP
